7.2. Titration Period

7.2.1. Baseline (Visit 2, Day 1)

The following procedures and assessments will be performed at the Visit 2:

- Review of inclusion and exclusion criteria.
- 4-hour video-EEG.
- Review and record seizure and meal diary.

- Dispense meal diary.
- Assessment of past/current AEDs and concomitant medications.
- Record vital signs (seated blood pressure, pulse rate, temperature, and respiration rate).
- Concomitant AED levels.
- Perform a brief neurological examination.
- If patient is in Cohort 2, dispense study drug for the Titration Period after eligibility is confirmed, and train patient/caregiver to administer and record treatments.
- Review AEs.

During the 5-day (for Cohort 2) Titration Period, the seizure diary should be completed daily. The meal diary should be completed for 24 hours prior to Visit 3. The investigator or designee will call or e-mail daily and record past/current AEDs, concomitant medications, and AEs.

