Urine pregnancy screen for post-menarchal females	X								
Physical Examination ^k	X								
Neurological Examination ^l	X	X		X	X		X	X	
Height/Weight	X			X			X	X	
CGI-I				X		X		X	
C-SSRS	X					X		X	
Dosing with Cannabidiol Oral Solution		X ^m	X	X	X	X	X ⁿ	X ^o	
Drug Accountability			X	X	X		X	X	
AEs	X	X	X	X	X	X	X	X	X
End of Study							X ^q		

^a Screening should occur within 28 (\pm 5) days.

^b Patients will have a Baseline 4-hour video EEG (including hyperventilation).

^c Follow-Up Period Visit (Visit 7) may be a phone call.

^d Hyperventilation testing will be conducted during the video-EEG.

^e Patients will return to the study clinic at Visit 5 or the Early Withdrawal Visit for a repeat 4-hour video-EEG.

^f Seizure diaries will be dispensed during the Screening Visit (Visit 1), reviewed and returned during Visits 2 through 5, and collected during Visit 6. A meal diary will be completed at Baseline (Visit 2); and for 24 hours before each PK sampling visit at Visit 3 and Visit 5 (Week 4, Day 6), or the Early Withdrawal Visit.

^g Vital signs will be taken after a 5-minute seated rest.

^h A urine dipstick pregnancy test will be performed on all female post-menarchal patients during Screening (Visit 1).

ⁱ Blood for pharmacokinetic analyses of CBD and 7-OH CBD will be drawn at Visit 3 (Day 1), Visit 5 (Week 4, Day 6), and Visit 6 (Week 4, Day 7). Blood draws will be taken pre-dose, 2, 4, and 6 hours after the morning dose (but before the next dose). In the Fed state (Visit 5, Week 4 Day 6), pre-dose blood samples should be collected BEFORE dosing with the “high-fat” breakfast (dose will be administered within 30 minutes of start of breakfast). In the Fasted state (Visit 6, Week 4 Day 7), patients will be fasted for 2 hours before the dose.

^j Trough values of CBD and 7-OH CBD will be collected at the Early Withdrawal Visit prior to dosing.

^k The physical examination will include evaluation of general appearance, skin, eyes, ears, nose, throat, neck, lymph nodes, chest, heart, abdomen, and extremities.

^l A complete neurological exam will be performed during Screening (Visit 1) and brief neurological examination (mental status, cranial nerves, nystagmus, motor system, sensory system, reflexes, coordination, gait, and station) will be performed at Visits 2 (Baseline), 3, 4, and 6 (End of Study) or the Early Withdrawal Visit.

^m Titration dose of study drug will be dispensed after patient qualification.

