1.3. Clinical Experience

A Phase 1/2 study to assess the pharmacokinetics (PK) and safety of multiple doses (10 mg/kg/day, 20 mg/kg/day, and 40 mg/kg/day) of pharmaceutical grade, synthetic Cannabidiol Oral Solution in 61 pediatric subjects with treatment-resistant seizure disorders aged 1 year to 17 years has been completed by the Sponsor (Protocol INS011-14-029). Subjects were exposed for a period of approximately 11 days before qualifying to participate in the long-term extension study (INS011-14-030). Analyses demonstrated that:

- Cannabidiol levels on Day 10 appeared to increase proportionally with weight-based dose across the dosing cohorts, notwithstanding the two different formulations of the investigational product.
- Steady-state levels of cannabidiol appeared to be attained with approximately 2 to 6 days of repeated BID dosing with Cannabidiol Oral Solution, with geometric mean area under the concentration-time curve in plasma during a dosing interval ($AUC_{0-\tau_{au}}$) of 507.0 (Cohort 1 [10 mg/kg/day]), 836.0 (Cohort 2 [20 mg/kg/day]), and 2108 ng·h/mL (Cohort 3 [40 mg/kg/day]) for all age categories combined.
- Geometric mean maximum plasma concentrations (C_{max}) of cannabidiol at steady-state were 91.0 (Cohort 1 [10 mg/kg/day]), 126.0 (Cohort 2 [20 mg/kg/day]), and 314.5 ng/mL (Cohort 3 [40 mg/kg/day]) for all age categories combined.
- Median time to maximum plasma concentration of cannabidiol at steady-state ranged from 2.0 to 3.0 hours for all age categories combined.

- Geometric means of cannabidiol apparent terminal half-life ($t_{1/2}$) ranged from 19.5 to 29.6 hours following a single dose of Cannabidiol Oral Solution for all age categories combined.
- Accumulation in cannabidiol exposures was approximately 3- to 4-fold for all age categories combined. Dosing cohort total geometric means ranged from 2.6 to 3.1 for accumulation ratio for C_{max} and from 3.6 to 4.4 for accumulation ratio for $AUC_{(0-\tau)}$.
- Most of the dosing cohort total variability in cannabidiol exposures after repeated dosing (Day 10) was lower than Day 1. Single and repeated administrations of Cannabidiol Oral Solution resulted in highly variable systemic exposures of cannabidiol.
- There were no apparent formulation-related differences observed in terms of $t_{1/2}$, dose-normalized exposures, and variability.

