3.1.1. Titration and Treatment Periods

Thirty patients in total will be enrolled into one of three dose cohorts; ten patients per cohort. Patients in Cohort 1 will be treated before patients are treated in Cohort 2, and patients in Cohort 2 will be treated prior to patients being treated in Cohort 3. Patients will be dosed approximately every 12 hours with food to help ensure consistent plasma levels are achieved, except for Visit 6 (Week 4, Day 7) when blood for fasting pharmacokinetic (PK) analysis will be drawn prior to the morning dose.

- Cohort 1: 20 mg/kg/day divided twice daily (BID) for 4 weeks.
- Cohort 2: Titration period of 20 mg/kg/day divided BID for 5 days, followed by 30 mg/kg/day divided BID for 4 weeks.
- Cohort 3: 10 mg/kg/day divided twice daily (BID) for 4 weeks. Eligible patients will be provided with their titration dose during their Baseline Visit (5 days at 20 mg/kg/day for Cohorts 2).

During the Treatment Period, patients will be dosed for 4 weeks during which the investigator will assess tolerability and effect. Patients will return to the site at the end of Week 2 (Visit 4) to evaluate medical status (seizure diary, vital signs, and neurological exam), clinical laboratory assessments, and assess AEs.

At Visit 5 (Week 4, Day 6), the patient will have a repeat 4-hour video-EEG including hyperventilation to count the number of absence seizures captured, and blood for PK analysis

Insys Development Company, Inc.
Protocol Number INS011-17-103

will be drawn. Blood for PK analyses will be drawn at Visit 3, Visit 5 (fed; Week 4, Day 6) and Visit 6 (fasted; Week 4, Day 7), or the Early Withdrawal Visit. The investigator will assess tolerability and efficacy.

Following the completion of the Treatment Period (Visit 6), patients will have the option to continue treatment in an open-label long-term safety study. Patients who choose to enroll in the long-term safety study will not have a follow-up phone call. Patients who do not choose to enroll in the long-term safety study will taper the dose of Cannabidiol Oral Solution according to the following schedule: doses between 20-30 mg/kg/day will be reduced to 20 mg/kg/day for five days and then discontinued; doses \leq 20 mg/kg/day can be discontinued without titration. This can be modified by the investigator based upon the patient's response. Patients will receive a follow-up phone call 14 days after completing Visit 6 (End of Study).

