7.3. Treatment Period

7.3.1. Visit 3 (Day 1)

The following procedures and assessments will be performed on Day 1:

- Review and record seizure diary and meal diary.
- Assessment of past/current AEDs and other concomitant medications.
- Record vital signs (seated blood pressure, pulse rate, temperature, and respiration rate).
- Collect blood samples (clinical chemistry and hematology, and PK sample)
- Perform a brief neurological examination.
- Record height and weight.
- Collect, review, and dispense Cannabidiol Oral Solution. If patient is in Cohort 1 (20 mg/kg/day) or Cohort 3 (10 mg/kg/day), train patient/caregiver to administer and record treatments.
- Dispense seizure diary.
- Investigator complete CGI-I.
- Review AEs.

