8.6.4.1. Adverse Events

The Medical Dictionary for Regulatory Activities (MedDRA, version 20.0 or higher) will be used to classify all AEs. Adverse event summaries will include only TEAEs, which will be summarized for each treatment group.

The number and percentage of subjects with AEs will be displayed for each treatment group by system organ class and preferred term. Summaries of AEs by severity and relationship to the IP will also be provided. Serious AEs (SAEs) and AEs resulting in discontinuation will be summarized separately in a similar manner. Patient listings of AEs and SAEs will be produced.

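### Daily adverse-event enquiry is planned only for Cohort 2's titration, so early adverse events are not equally ascertained across the dose cohorts

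*Protocol*

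**What the plan says.** Section 7.2.1 supplies drug at Visit 2 to one cohort: "If patient is in Cohort 2, dispense study drug for the Titration Period after eligibility is confirmed". The paragraph on follow-up in that period opens "During the 5-day (for Cohort 2) Titration Period, the seizure diary should be completed daily" and ends "The investigator or designee will call or e-mail daily and record past/current AEDs, concomitant medications, and AEs".

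The other two cohorts have no titration. Section 7.3.1 has them begin at Visit 3: "If patient is in Cohort 1 (20 mg/kg/day) or Cohort 3 (10 mg/kg/day), train patient/caregiver to administer and record treatments". For all cohorts the next contact is given in Section 3.1.1: "Patients will return to the site at the end of Week 2 (Visit 4) to evaluate medical status". AEs are reviewed at Visits 3, 4, 5 and 6 (Sections 7.3.1 to 7.3.4).

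The Call/Email column of Table 1 lies under the Titration Period and names no cohort. It allows a span of either 5 or 10 days, and no current cohort has a 10-day titration.

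On analysis, Section 8.6.4.1 restricts AE summaries to TEAEs and continues: "The number and percentage of subjects with AEs will be displayed for each treatment group by system organ class and preferred term". Section 6.2.8.1 starts TEAE monitoring at dosing. The Synopsis and Section 8.2 instead equate TEAEs with events in the Treatment Period.

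**The concern.** Cohort 2 spends its first five days on 20 mg/kg/day with a daily enquiry about AEs. Cohort 1 starts on the same dose without one, and so does Cohort 3 at 10 mg/kg/day. These are the days when exposure is rising. Section 1.3 reports "Steady-state levels of cannabidiol appeared to be attained with approximately 2 to 6 days of repeated BID dosing", with roughly 3- to 4-fold accumulation; Section 1.3.1 gives 2 to 4 days and about 2-fold.

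Somnolence and diarrhea are AEs of special interest (Section 6.2.8.1) and rose with dose in the earlier study (Section 1.3). Mild, short-lived events of this kind are the ones most likely to depend on how soon someone asks. Transaminase elevations, the third such event, are found by scheduled blood tests and are not affected.

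The study is open-label, cohorts are filled in sequence with 10 patients each, and safety is described without inference. The TEAE percentages by cohort are therefore the tolerability evidence for comparing doses, and one patient moves a percentage by 10 points.

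**Working it through.** The protocol gives no AE rate or detection figure on this point, so there is nothing to reproduce. The check is a count of planned AE enquiries, followed by an illustration.

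**Inputs.** Visit 3 is Day 1 of the Treatment Period. Visit 4 is taken as treatment day 14 (end of Week 2), Visit 5 as day 3 × 7 + 6 = 27, and Visit 6 as day 28. Cohort 2 has 5 earlier days on drug, each with one call or e-mail, so 5 is added to each of its visit days.

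| | Cohorts 1 and 3 | Cohort 2 |
|---|---|---|
| Calls, by day since first dose | none | 1, 2, 3, 4, 5 |
| Visits 3, 4, 5, 6 | 1, 14, 27, 28 | 6, 19, 32, 33 |
| Enquiries in first 14 days | 2 | 5 + 1 = 6 |
| Enquiries over all dosing | 4 in 28 days | 5 + 4 = 9 in 33 days |
| Gap from Visit 3 to Visit 4 | 14 − 1 = 13 days | 19 − 6 = 13 days |

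**Does Visit 3 count for Cohorts 1 and 3?** Table 1 marks dosing at Visit 3, and its footnote on pharmacokinetic sampling lists Visit 3 and then states: "Blood draws will be taken pre-dose, 2, 4, and 6 hours after the morning dose (but before the next dose". On that text the children are on site for hours after their first dose. Section 7.3.1 lists only a single sample, and the timed sampling table in Section 6.2.9 covers Visits 5 and 6 only. If Visit 3 precedes the first dose, the counts for Cohorts 1 and 3 fall to 1 in the first 14 days and 3 overall.

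**Effect of the TEAE window.**
- *From first dose (Section 6.2.8.1):* the five call days count. Cohort 2 has closer enquiry early on and 33 − 28 = 5 more days at risk. Any artefact raises the 30 mg/kg/day cohort.
- *Treatment Period only (Synopsis, Section 8.2):* the calls fall outside the window, and planned contacts inside it are the same in all cohorts (Visits 3 to 6). But Cohort 2's first 5 days on drug are then left out, while those of Cohorts 1 and 3 count. Any artefact tends to lower Cohort 2.

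Early events are not like for like under either reading.

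**Illustration, first-dose window (all values assumed).** Suppose the same true incidence of transient early AEs in every cohort, detected with probability 0.9 under daily enquiry and 0.5 to 0.9 under two-week recall. Observed rate = incidence × detection.
- Incidence 30%: 0.30 × 0.9 = 27% against 0.30 × 0.5 = 15% up to 27%; artefact 0 to 12 points.
- Incidence 50%: 0.50 × 0.9 = 45% against 0.50 × 0.5 = 25% up to 45%; artefact 0 to 20 points.

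With 10 patients, an observed 3 of 10 has an exact 95% interval of 7% to 65%. An artefact of this size could not be told apart from chance or from a dose effect.

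**The case against.** The strongest reply is that the imbalance is modest and may not reach the tables. AEs in the gap are not lost: every study period is covered by AE documentation (Section 3.1.3), and Visit 4 reviews them. Cohort 2 has the same 13-day gap after its step to 30 mg/kg/day, so the gap itself is common to all cohorts. If TEAEs cover the Treatment Period only, events confined to the call days are not tabulated at all. Linking contact to titration is a coherent choice, doses up to 40 mg/kg/day were reported as generally well tolerated without titration (Section 1.5), and safety data are reviewed on an ongoing basis (Section 6.2.8.9).

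Much of this stands. A reader might infer that AE rates are simply not comparable between doses, that Cohorts 1 and 3 have no AE collection for two weeks, or that Cohort 2's rate is bound to be inflated. The documents support none of these. Collection continues by recall, the protocol gives no figure for how much recall loses, and inflation follows only from the first-dose window.

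What the reply does not remove is the difference in the first days on drug. A reason to contact Cohort 2 daily is not a reason to record AEs differently in the cohorts it is set beside. The Treatment Period reading replaces unequal enquiry with unequal exclusion of early days.

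**Conclusion.** The point holds as one of unequal early ascertainment: about 6 planned AE enquiries in the first 14 days on drug in Cohort 2, against 2 (or 1) in Cohorts 1 and 3, with TEAEs tabulated by cohort. This count rests on one contact per titration day and on visits at their nominal times.

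The size of the resulting bias is unknown. Under the assumed detection values it runs from nothing to 20 percentage points, and its sign depends on which TEAE definition is applied. It is a cheap improvement to data collection, not a flaw that invalidates the safety comparison. No position is taken on dosing or clinical management.

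**What to change.** 1. In Sections 7.2.1 and 7.3.1 and the Call/Email column of Table 1, tie the daily AE enquiry, as data collection, to the first 5 days of dosing in every cohort. Correct the column's time span, which matches no current cohort.
2. Reconcile Section 6.2.8.1 with the Synopsis and Section 8.2 on a single TEAE window starting at first dose.
3. If Cohort 1 has already been treated, apply the change to Cohort 3. Present TEAEs in all cohorts by time since first dose, show Cohort 2's titration-period events separately, and state that Cohort 1 was ascertained differently. Cohort 2's events should not be dropped, since that would delete true events from one cohort only.

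With the change, planned enquiries over dosing become 4 + 5 = 9 in Cohorts 1 and 3, as in Cohort 2 (8 if Visit 3 precedes the first dose). The 13-day gap after Cohort 2's step to 30 mg/kg/day remains.

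The cost is at most 20 patients × 5 days = 100 short calls or e-mails by existing site staff, or 10 × 5 = 50 if only Cohort 3 can be changed. No visit or test is added.

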7.3. Treatment Period

7.3.1. Visit 3 (Day 1)

The following procedures and assessments will be performed on Day 1:

- Review and record seizure diary and meal diary.
- Assessment of past/current AEDs and other concomitant medications.
- Record vital signs (seated blood pressure, pulse rate, temperature, and respiration rate).
- Collect blood samples (clinical chemistry and hematology, and PK sample)
- Perform a brief neurological examination.
- Record height and weight.
- Collect, review, and dispense Cannabidiol Oral Solution. If patient is in Cohort 1 (20 mg/kg/day) or Cohort 3 (10 mg/kg/day), train patient/caregiver to administer and record treatments.
- Dispense seizure diary.
- Investigator complete CGI-I.
- Review AEs.

7.3.2. Visit 4 (Week 2)

The following procedures and assessments will be performed:

- Review and record seizure diary.
- Assessment of past/current AEDs and other concomitant medications.

- Record vital signs (seated blood pressure, pulse rate, temperature, and respiration rate).
- Collect blood samples (clinical chemistry and hematology).
- Perform a brief neurological examination.
- Review AEs.
- Collect, review, and dispense Cannabidiol Oral Solution.
- Dispense meal and seizure diary.

7.3.3. Visit 5 (Week 4, Day 6)

The patient should complete their meal diary for 24 hours prior to Visit 5, bring their morning dose of the IP with them to the study site and should not eat breakfast. The following procedures and assessments will be performed:

- Review and record seizure and meal diaries.
- 4-hour video-EEG.
- Assessment of past/current AEDs and other concomitant medications.
- PK blood draws will be taken pre-dose, 2, 4, and 6 hours after the morning dose (but before the next dose). The pre-dose blood sample should be collected BEFORE dosing with “high-fat” breakfast (dose will be administered within 30 minutes of start of breakfast).
- Dosing with Cannabidiol Oral Solution.
- Investigator complete CGI-I.
- Complete C-SSRS
- Review AEs.

7.3.4. End of Study: Visit 6 (Week 4, Day 7)

The patient should bring their morning dose of medications with them to the study site and should not eat for at least two hours prior to arrival. The following procedures and assessments will be performed:

- Record vital signs (seated blood pressure, pulse rate, temperature, and respiration rate).
- Draw blood for clinical laboratory tests (clinical chemistry and hematology) and concomitant AED level.
- PK blood draws will be taken pre-dose, 2, 4, and 6 hours after the morning dose (but before the next dose). Patient will be fasted for 2 hours before dose. A standard breakfast will be provided 2 hours after the dose, AFTER the 2-hour blood draw.
- Dosing with Cannabidiol Oral Solution (patient should not eat until two hours after dose and the 2-hour PK blood is drawn).

- Collect urine sample for urinalysis.
- Perform 12-lead ECG.
- Perform a brief neurological examination.
- Record height and weight.
- Review AEs.

7.4. Early Withdrawal Visit

The patient should complete their seizure diary for 7 days prior to the visit, complete their meal diary for 24 hours prior to the visit, and bring their morning dose of the medications with them to the study. The following procedures and assessments will be performed at Visit 7 or following patient withdrawal:

- 4-hour video-EEG.
- Review and collect seizure and meal diaries.
- Review and collect meal diary.
- Assessment of past/current AEDs and other concomitant medications.
- Concomitant AED levels.
- Record vital signs (seated blood pressure, pulse rate, temperature, and respiration rate).
- Collect blood samples (clinical chemistry and hematology).
- 12-lead ECG.
- PK blood sample.
- Collect urine sample for urinalysis.
- Perform a brief neurological examination.
- Record height and weight.
- Investigator complete CGI-I.
- Complete C-SSRS.
- Review/Collect Cannabidiol Oral Solution.
- Review AEs.

7.5. Visit 7 (Follow-Up Period)

For patients who do not choose to enroll in the long-term safety study, the following assessments will be performed by phone call at 14 days after completion of Visit 6 (End of Study):

- Record past/current AEDs and other concomitant medications.
- Review AEs.

8. STATISTICS

8.1. Efficacy Endpoints

- % change in absence seizure counts comparing treatment at Week 4 (Visit 5) video-EEG to Baseline (Visit 2) video-EEG and comparing doses.
- % change in time to absence seizure during hyperventilation testing on video-EEG comparing treatment at Week 4 (Visit 5) to Baseline (Visit 2) and comparing doses.
- % patients seizure free at Week 4 (Visit 5) based on seizure diary, comparing doses.
- Investigator CGI-I at Week 4 (Visit 5) comparing doses.

8.2. Safety Endpoints

Changes in safety endpoints will be reported as mean/median change from baseline at relevant time points and as a listing of events that fall outside normal limits.

- Incidence, type, and severity of AEs and serious adverse events (SAEs) occurring during the Treatment Period (i.e., treatment-emergent AEs [TEAEs]).
- Changes from Baseline (Visit 2) in vital signs during the Treatment Period.
- Changes from Screening in laboratory values (hematology, chemistry, and urinalysis) during the Treatment Period.

8.3. Pharmacokinetic Endpoints

- C_{max} and dose-normalized C_{max} : fed (Visit 5 [Week 4, Day 6]) and fasted (Visit 6 [Week 4, Day 7]).
- Area under the plasma concentration curve ($AUC_{(0-t)}$) and dose normalized area under the curve ($AUC_{(0-t)}/Dose$): fed (Visit 5 [Week 4, Day 6]) and fasted (Visit 6 [Week 4, Day 7]).
- Trough plasma concentration (C_{trough}) and dose normalized trough plasma concentration ($C_{trough}/Dose$): fed (Visit 5 [Week 4, Day 6]) and fasted (Visit 6 [Week 4, Day 7], Visit 3, or the Early Withdrawal Visit).

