The investigational product will be dosed orally in three dose cohorts. Total daily doses of 10, 20, or 30 mg/kg/day will be administered in two daily doses of 5, 10, or 15 mg/kg/dose. Doses higher than 20 mg/kg/day will be titrated. Cannabidiol Oral Solution will be administered with food except for when fasting PK values will be obtained (Visit 6 [Week 4, Day 7]).

Duration of treatment:

The maximum duration of the study from screening to the follow-up of AEs call will be approximately 10 weeks.

Reference therapy, dosage and mode of administration:

Not applicable.

Criteria for evaluation:**Efficacy Endpoints**

- % change in absence seizure counts comparing treatment at Week 4 (Visit 5) video-EEG to Baseline (Visit 2) video-EEG and comparing doses.
- % change in time to absence seizure during hyperventilation testing on video-EEG comparing treatment at Week 4 (Visit 5) to Baseline (Visit 2) and comparing doses.
- % patients seizure free at Week 4 (Visit 5) based on seizure diary, comparing doses.
- Investigator CGI-I at Week 4 (Visit 5) comparing doses.

Safety Endpoints

- Incidence, type, and severity of AEs and serious adverse events (SAEs) occurring during the Treatment Period (i.e., treatment-emergent adverse events [TEAEs]).
- Incidence, type, timing, and severity of AEs and serious adverse events (SAEs) occurring during the Safety Period. (i.e., treatment-emergent adverse events [TEAEs]).
- Changes from Baseline (Visit 2) in vital signs during the Treatment Period.
- Changes from Screening (Visit 1) in laboratory values (hematology, chemistry, and urinalysis) during the Treatment Period.

Pharmacokinetic Endpoints

- C_{max} and dose-normalized C_{max} : fed (Visit 5 [Week 4, Day 6]) and fasted (Visit 6 [Week 4, Day 7]).

- Area under the plasma concentration curve (AUC_{0-t}) and dose normalized area under the curve (AUC_{0-t} /Dose): fed (Visit 5 [Week 4, Day 6]) and fasted (Visit 6 [Week 4, Day 7]).
- Trough plasma concentration (C_{trough}) and dose normalized trough plasma concentration (C_{trough}/Dose): fed (Visit 5 [Week 4, Day 6]), and fasted (Visit 6 [Week 4, Day 7]), Visit 3, or the Early Withdrawal Visit.

Statistical Methods:

Efficacy Analysis

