4. TREATMENTS

4.1. Treatments Administered

In the Treatment Period, Cannabidiol Oral Solution will be dosed orally in three dose cohorts. Patients or parent/caregiver will be instructed how to measure, take their dose, and record their dose in the dosing diary when the IP is dispensed for the first time.

Total daily doses of 10, 20, or 30 mg/kg/day will be administered with food in two daily doses of 5, 10, or 15 mg/kg/dose approximately every 12 hours. Patients in Cohort 1 will be treated prior to initiation of enrollment into Cohort 2, and patients in Cohort 2 will be treated prior to initiation of enrollment into Cohort 3. Doses higher than 20 mg/kg/day will be titrated as described in [Section 4.4](#). Cannabidiol Oral Solution will be administered within 30 minutes after a meal, except during Visit 6 when fasting PK values will be obtained.

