4.3. Method of Assigning Subjects to Treatment Groups

Eligible patients will be sequentially assigned to each dose cohort. That is, the first 10 eligible patients will be in Cohort 1, and so on.

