4.4. Selection and Timing of Dose for Each Subject

Ten patients will be enrolled in each of three dose cohorts:

- Cohort 1: 20 mg/kg/day divided BID for 4 weeks.
- Cohort 2: 20 mg/kg/day divided BID for 5 days followed by 30 mg/kg/day divided BID for 4 weeks.
- Cohort 3: 10 mg/kg/day divided BID for 4 weeks.

Subjects will take each dose approximately every 12 hours with food in order to ensure consistent plasma levels are achieved, except for Visit 6 when blood for fasting pharmacokinetic analysis will be drawn prior to the morning dose. The date and time of all investigational product administrations will be documented in the case report form (CRF) from the seizure diary.

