8.6.6. Pharmacokinetic Analyses

Descriptive statistics of trough plasma concentration and PK parameters data for CBD and 7-OH CBD by Visit, Dose, and Response will be provided. The following noncompartmental PK parameters will be estimated from the plasma concentration-time data: area under the curve from time 0 to the last measured concentration (AUC_{0-t}) by maximum plasma concentration (C_{max}), and time to reach maximum plasma concentration (T_{max}) using Phoenix WinNonlin (Version 6.3 or higher; Pharsight Corporation, Cary, NC 27518, USA). Additional PK parameters may be estimated, as appropriate. Exploratory analysis of dose (exposure)-response relationship will be performed. Further population PK approach may be used for PK parameter estimation, as appropriate.

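### The Visit 3 trough endpoint has no cohort limit, although Cohorts 1 and 3 first receive drug at Visit 3: 20 of 30 planned values are pre-drug samples, not troughs

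*Protocol*

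**What the plan says.** Section 8.3 makes C_trough and its dose-normalised form endpoints at "fed (Visit 5 [Week 4, Day 6]) and fasted (Visit 6 [Week 4, Day 7], Visit 3, or the Early Withdrawal Visit". The synopsis has the same endpoint: "and fasted (Visit 6 [Week 4, Day 7]), Visit 3, or the Early Withdrawal Visit". The two differ in where the bracket closes, so section 8.3 literally puts Visit 3 among the fasted visits and the synopsis does not. Neither limits Visit 3 to a cohort, and Table 1 marks a Visit 3 PK sample without distinguishing cohorts.

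Section 8.6.6 states the use of these data: "Descriptive statistics of trough plasma concentration and PK parameters data for CBD and 7-OH CBD by Visit, Dose, and Response will be provided".

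The dosing schedule is set elsewhere in the protocol:

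- Section 7.2.1, at Visit 2: "If patient is in Cohort 2, dispense study drug for the Titration Period after eligibility is confirmed".
- Section 4.4: "Cohort 2: 20 mg/kg/day divided BID for 5 days followed by 30 mg/kg/day divided BID for 4 weeks". Cohorts 1 and 3 have no titration step.
- Section 7.3.1, at Visit 3, headed as Day 1: "If patient is in Cohort 1 (20 mg/kg/day) or Cohort 3 (10 mg/kg/day), train patient/caregiver to administer and record treatments".
- Section 4.1 ties that training to first dispensing; patients or caregivers are taught to measure, take and "record their dose in the dosing diary when the IP is dispensed for the first time".

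**The concern.** A trough is the concentration at the end of a dosing interval, so it needs an earlier dose. In Cohorts 1 and 3 there is none before the Visit 3 pre-dose sample. Other cannabinoids are excluded for 30 days before Screening (exclusion criterion 16) and prohibited from Screening onward (section 4.7.2), so these samples should hold essentially no CBD. They show the pre-drug state and carry no information about exposure at 10 or 20 mg/kg/day.

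The endpoint line nevertheless calls them C_trough and divides them by dose. An analyst who follows sections 8.3 and 8.6.6 as written would produce a Visit 3 trough row with near-zero entries under two doses and real concentrations from the third cohort. That contrast comes from the dispensing schedule and says nothing about dose and exposure.

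**Working it through.** **Inputs**

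- Enrolment: three cohorts of 10 (sections 3.1.1 and 4.4), filled in sequence, so that "the first 10 eligible patients will be in Cohort 1, and so on" (section 4.3). 3 × 10 = 30, which matches the protocol's stated total.
- Timing of Visit 3: Day 1 with a window of 0 days in Table 1; Day 1 in Table 1 footnote i and in section 7.3.1. Section 3.1.3 and the synopsis also label it Week 1, which does not change when drug is first dispensed.
- Pre-dose sampling at Visit 3: Table 1 footnote i only. Section 7.3.1 says just that a PK sample is taken, and the sampling-time table in section 6.2.9 covers Visits 5 and 6. The 2, 4 and 6 hour draws in footnote i are post-dose and are not troughs.

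**Classification of the Visit 3 pre-dose sample**

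| Cohort | Treatment dose (mg/kg/day) | Drug taken before Visit 3 | n | What the sample is |
|---|---|---|---|---|
| 1 | 20 | none | 10 | pre-drug |
| 2 | 30 | 20 mg/kg/day for 5 days | 10 | trough at 20 mg/kg/day |
| 3 | 10 | none | 10 | pre-drug |

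**Counts**

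- Pre-drug: 10 + 10 = 20; 20/30 = 66.7%.
- Valid troughs: 10; 10/30 = 33.3%.
- Pre-dose values at Visits 5 and 6, after about 4 weeks on the treatment dose: 2 × 30 = 60, none affected.

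**Is the Cohort 2 value a usable trough?** Section 1.3 reports steady state after roughly 2 to 6 days of twice-daily dosing, and single-dose half-lives of 19.5 to 29.6 hours. Five days is 120 hours. Under simple first-order accumulation, the fraction of steady state reached is 1 − 0.5^(120/t½):

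- t½ = 19.5 h: 0.986
- t½ = 29.6 h: 0.940

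So it is a near-steady-state trough at the dose actually taken.

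**What the Visit 3 row would show under section 8.6.6**

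- *Grouped by cohort dose:* the 10 and 20 mg/kg/day cells hold 10 pre-drug values each. The 30 mg/kg/day cell holds 10 troughs that were produced by 20 mg/kg/day.
- *Grouped by dose taken:* the Cohort 2 troughs move to 20 mg/kg/day. Cohort 1 has only one dose, 20 mg/kg/day, so unless its samples are coded as pre-drug they can fall in the same cell: 10 pre-drug values with 10 real troughs. If the pre-drug values were set to zero (an assumption; the protocol gives no rule) and the Cohort 2 mean were m, the cell mean would be (10 × 0 + 10 × m)/20 = m/2.

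**The case against.** **The analysis plan can sort this out.** A statistical or PK analysis plan commonly decides how pre-first-dose and unquantifiable samples are handled, and anyone who knows the schedule would recognise these values. That is fair, and it is one reason the point is minor. But the endpoint and the dispensing schedule are both fixed in this protocol and they conflict here, so this is not a detail left for later.

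**Drug might have been given earlier.** Section 7.3.1 mentions collecting drug at Visit 3. That fits Cohort 2, the only cohort the protocol supplies at Visit 2.

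**The protocol never says all cohorts.** Correct. The reading rests on the absence of any cohort limit in section 8.3, the synopsis and Table 1.

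**A pre-drug sample is useful.** Agreed, as a blank. The fault lies in naming it a trough and normalising it by dose, not in drawing it.

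Three stronger readings are tempting, and the protocol does not support them:

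- *That Cohort 2 is also wrong, because its Visit 3 value reflects 20 and not 30 mg/kg/day.* Nothing in the protocol requires a Visit 3 trough at the cohort's final dose. The value is valid at the dose taken.
- *That C_trough/Dose in Cohort 2 will be one third too low.* That would happen only if the value were divided by 30 (20/30 = 0.667). The protocol names no divisor, so this is hypothetical.
- *That the trough endpoint cannot be delivered in two cohorts, or that an early trough must be added at Visit 4.* The endpoint also covers Visits 5 and 6, where every cohort contributes. No section calls for an early trough at the treatment dose.

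**Conclusion.** The point holds, and it is minor. As written, the Visit 3 part of the trough endpoint has no meaning in Cohorts 1 and 3: 20 of 30 planned values (67%) are pre-drug. The remaining 10, in Cohort 2, are sound troughs at 20 mg/kg/day. The damage is confined to the Visit 3 row of a descriptive summary serving a secondary objective. The 60 planned troughs at Visits 5 and 6, C_max and AUC are untouched, and the PK objective can still be answered.

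The counts assume full enrolment, a pre-dose sample from every patient at Visit 3, and no withdrawal before then. That the pre-drug samples will be near zero is an expectation from the cannabinoid restrictions, not a stated result.

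**What to change.** Reword the trough endpoint in section 8.3 and the synopsis along these lines:

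> C_trough and C_trough/Dose at Visit 3: Cohort 2 only, after 5 days at 20 mg/kg/day, reported at and normalised by 20 mg/kg/day. Visit 3 pre-dose samples in Cohorts 1 and 3 are pre-drug; they are listed as such and excluded from trough summaries.

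The cost is an edit in two places. Blood draws, visits and Table 1 stay as they are, and no Visit 4 sample is added. The Cohort 1 and 3 pre-dose samples are still drawn, so the check for CBD before treatment is kept. The Visit 3 trough summary then rests on 10 values, which are the only real troughs the schedule yields at that visit.
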